T2DM according to ADA criteria	subjects must be in good general health as determined by physical exam, medical history, blood chemistries, CBC, TSH, EKG and urinalysis 18-70 years old 21-45 kg/m Male and Female $\geq 7.0\%$ and \leq up to 10.5% Drug naïve and/or on a stable dose (more than 3 months) of metformin and/or sulfonylurea	Subjects who are Type 1 Diabetes, have proliferative diabetic retinopathy, plasma creatinine >1.4 females or >1.5 males will be excluded. Subjects taking drugs known to affect glucose metabolism (other than metformin and sulfonylurea)

Item 6

Research Plan / Description of the Research Methods *a. Provide a comprehensive narrative describing the research methods. Provide the plan for data analysis (include as applicable the sample size calculation).*

Step-by-Step Methods:

After screening, eligible subjects will receive a measurement of endogenous glucose production (EGP) with a prime-continuous infusion of 3-³H-glucose. The EGP measurement will be performed in the morning after a 10-12 hour overnight fast and will last 8.5 hours (from 6 AM to 2:30 PM). After a 3.5-hour tracer equilibration period, subjects (20 per group) will receive one of the following medications: (i) placebo; (ii) exenatide 5 ug subcutaneously; (iii) dapagliflozin (10 mg); and (iv) dapagliflozin 10 mg plus exenatide 5 ug (see flowsheet for EGP). Following the test medication at 9:30 AM, blood samples will be drawn every 15 minutes for an additional 5 hours and plasma glucose, insulin, C-peptide, glucagon, and glucose specific activity will be measured.

Visit 1: Screening. Medical history will be obtained and physical exam will be performed. Blood will be drawn for FPG, routine blood chemistries, CBC, lipid profile, HbA1c, and thyroid function. Urinalysis, EKG, albumin/creatinine ratio and pregnancy test will be performed.

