Visit 2: Endogenous Glucose Production Measurement: The rate of endogenous glucose production will be measured with 3-³H-glucose infusion. [3-³H]-glucose infusion will be started at 6 AM and continued until 2:30 PM (5 hours after drug administration). At 6 AM a catheter will be placed into an antecubital vein and a prime (40 uCi x FPG/100)-continuous (0.4 uCi) infusion of [3-³H]- glucose will be started and continued until 2:30 PM. (5 hours after drug administration). Participant's hand will be placed in a box heated to 50-60°C (122-140°F). Baseline blood samples will be obtained at -210, -60, -50, -45, -40, -35, -30, -20, -10, and 0. After 3.5 hours of tracer equilibration blood samples will be obtained every 10-20 minutes from 9:30 AM to 2:30 PM. Plasma glucose, insulin, C-peptide, glucagon, and [3-³H]-glucose specific activity will be measured. Urine will be collected from 6 to 9:30 AM and from 9:30 AM to 2:30 PM. Urinary volume and glucose concentration will be measured and urinary glucose excretion rate calculated. The study will end at 2:30 PM. The total amount of blood taken during this time is 164 ml or 12 tablespoons.

Visit 3: Double Tracer Oral Glucose Tolerance Test (DT-OGTT): Within one to two weeks after the measurement of EGP, all subjects will have a 5-hour DT-OGTT with measurement of plasma glucose, insulin (I), C-peptide (CP), and glucagon concentrations at -180, -6, -5, -45, -40, -35, -30, -20, -10, 0 and every 15-30 minutes thereafter to obtain a measure of overall glucose tolerance, insulin secretion ($\frac{\text{ICPO-120}}{\text{IGO-120}}$), insulin sensitivity (Matsuda index [MI]), beta cell function, ($\frac{\text{ICPO-120}}{\text{IGO-120}} \times \text{MI}$), and suppression of plasma glucagon concentration (64). At 7 AM a catheter will be placed into an antecubital vein and a prime (25 uCi x FPG/100)-continuous (0.25 uCi) infusion of [3-³H]-glucose will be started and continued until 3 PM. Urinary volume and glucose concentration will be measured and urinary glucose excretion rate calculated. The total amount of blood taken during the OGTT is 226 ml about 15 tablespoons. HbA1c will be measured twice, once on the day of the DT-OGTT and once on the day of the EGP measurement.

Note: *The repeated double tracer listed in the grant application will not be performed as part of this protocol. The grant will be amended to remove at continuing review of the grant application.*

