Data Analysis Plan: The primary end point is the change in EGP. The difference in rate of EGP during the last hour of the study (from 240-300 minutes) between drug-treatment and placebo treatment studies represents the effect of drug treatment on EGP, which will be compared among the 3 drug treatments (exenatide; dapagliflozin; exenatide plus dapagliflozin) with ANOVA. Post hoc testing will be performed with Bonferroni correction for multiple comparisons. The following primary comparison will be performed: (i) change in EGP above baseline following dapagliflozin alone versus dapagliflozin/exenatide.

Item 7 Risks Section:

Complete the following table to describe the risks of all **research procedures** listed in Step 2, Institutional Form (items 28-34). *Do not list risks of Routine care procedures here.*

N/A, Risks are described in the informed consent document – do not complete this table.

Research procedures	Risks
example: 
• History and physical• Questionnaire• Laboratory tests Add or delete rows as needed	List the reasonably expected risks under the following categories as appropriate:
Chart Review	
Serious and likely;
 
○ Insert risk here or enter "none" 
Serious and less likely;
 
○ Insert risk here or enter "none" 
Serious and rare;
 
○ Insert risk here or enter "none" 
Not serious and likely;
 
○ Insert risk here or enter "none" 
Not serious and less likely
 
○ Breach of confidentiality

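### The primary EGP comparison is valid but ignores pre-dose plasma glucose, a likely prognostic factor already measured; adjusting for it is a cheap gain of uncertain size

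*Combined protocol and SAP*

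**What the plan says.** The Data Analysis Plan in Item 6 defines the drug effect as "The difference in rate of EGP during the last hour of the study (from 240-300 minutes) between drug-treatment and placebo treatment studies". This is to be "compared among the 3 drug treatments (exenatide; dapagliflozin; exenatide plus dapagliflozin) with ANOVA", and "Post hoc testing will be performed with Bonferroni correction for multiple comparisons". The single named primary comparison is the "change in EGP above baseline following dapagliflozin alone versus dapagliflozin/exenatide". No covariate or stratification factor is named.

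The wording about drug and placebo studies could suggest a within-subject contrast. However, Item 2 gives each subject one EGP measurement, and Item 6 states that "subjects (20 per group) will receive one of the following medications". The groups are therefore parallel, and variation between subjects enters the primary comparison in full.

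Three other places bear on the point:

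- Item 5 admits subjects over a range of 7.0% to 10.5%. The label is missing from the text, and the range is read here as HbA1c.
- Item 6, Visit 2, says "Baseline blood samples will be obtained at -210, -60, -50, -45, -40, -35, -30, -20, -10, and 0" and lists plasma glucose among the measurements. Nine of those times lie between −60 and 0 min.
- Items 3 and 4 attribute the rise in EGP under SGLT2 inhibition to glucosuria.

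**The concern.** A population this wide in glycaemia will differ considerably in plasma glucose on the study morning. If glucosuria triggers the EGP response, and a subject with higher glucose loses more glucose in urine on the same treatment, then pre-dose glucose predicts how large the response will be. The second step is physiological inference. The documents supply only the step from glucosuria to EGP.

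Subtracting baseline EGP does not deal with this. It removes additive differences in EGP level, not differences in the size of the response.

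Two things are at stake in a comparison of 20 with 20. Variance that could be explained stays in the error term. And if the two dapagliflozin arms happen to differ in starting glucose, the estimated exenatide effect is shifted with no correction. Because the covariate is measured before dosing, treatment cannot have altered it, which is not true of post-dose plasma or urine glucose.

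**Working it through.** **Inputs.** From the documents: 20 per group (Item 6). The form asks authors to "include as applicable the sample size calculation", but no alpha, power, effect size or SD appears, so the figure of 20 cannot be reproduced. Assumed here: two-sided alpha 0.05, random allocation, and a within-arm correlation r between pre-dose glucose and EGP change, varied from 0 to 0.7. The outcome and the covariate are each expressed in units of their own SD.

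**Starting point.** The SE of the unadjusted contrast is √(2/20) = 0.316 SD. By the noncentral t with 38 df, 80% power corresponds to a true difference of 0.909 SD (noncentrality 0.909/0.316 = 2.87). This effect is back-solved from n = 20; it is not a figure from the plan. At an assumed Bonferroni level of 0.05/3 the detectable difference would be 1.06 SD.

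**Adjusted, common slope.** Residual variance is multiplied by (1 − r²), estimating the slope inflates variance by (1 + 1/36), and df fall to 37:

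noncentrality = 0.909 / √[(1 − r²)(1 + 1/36)(2/20)]

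At r = 0.5 this is 0.909/√(0.75 × 1.0278 × 0.1) = 3.27, giving 89.0% power.

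**Adjusted, slope abolished by exenatide.** If the slope is r under dapagliflozin alone and zero under the combination, with total variance equal in the two arms, a pooled slope estimates r/2. It then removes only r²/4 of the variance. At r = 0.6 the factor is 1 − 0.09 = 0.91, the noncentrality is 2.97 and power is 82.5%.

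| r | Equivalent n per arm, 20/(1 − r²) | Power, common slope | Power, slope abolished in combination arm |
|---|---|---|---|
| 0 | 20.0 | 78.9% | 78.9% |
| 0.2 | 20.8 | 80.5% | 79.3% |
| 0.3 | 22.0 | 82.5% | 79.8% |
| 0.4 | 23.8 | 85.4% | 80.5% |
| 0.5 | 26.7 | 89.0% | 81.4% |
| 0.6 | 31.2 | 93.2% | 82.5% |
| 0.7 | 39.2 | 97.2% | 83.8% |

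With a common slope, adjustment breaks even with the unadjusted 80% at about r = 0.17. Simulation agrees: common-slope power was 82.9% at r = 0.3 and 89.1% at r = 0.5. With the slope abolished it was 79.9%, 81.8% and 82.8% at r = 0.3, 0.5 and 0.6.

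**Imbalance.** Under random allocation the difference in mean pre-dose glucose between two arms of 20 has SE 0.316 SD. The chance that it exceeds 0.5 SD is 2[1 − Φ(0.5/0.316)] = 11.4%. With a common slope, an imbalance of 0.5 SD shifts the unadjusted contrast by 0.5r: 0.15 SD at r = 0.3 and 0.25 SD at r = 0.5. The latter is 0.25/0.909 = 27% of the reference effect.

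**Validity.** In simulations of 20,000 null trials per setting, the unadjusted test rejected in 4.6% to 5.1% for r from 0 to 0.7.

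**The case against.** The strongest reply is that nothing here is an error. The unadjusted comparison holds its type I error, its SE already allows for chance imbalance, and a shift of 0.25 SD is less than one SE. That stands. The point concerns precision and the estimate conditional on the imbalance that actually occurs, not a faulty test.

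The second reply is that the gain is assumed, since no correlation is documented. Below about r = 0.17 adjustment gains nothing. The trial's own hypothesis also works against a large gain: if exenatide prevents the EGP rise, it should flatten the slope in the combination arm, and the last column of the table then applies. This stands too, and it is why the common-slope figures are an upper case. If pre-dose EGP is also adjusted for, the relevant quantity is a partial correlation. An assumed partial r of 0.2 to 0.4 removes 4% to 16% of the remaining variance under a common slope.

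A reader might infer two stronger things. One is that the tracer prime makes fasting glucose a confounder, because Visit 2 uses "a prime (40 uCi x FPG/100)-continuous (0.4 uCi) infusion" and only the prime is scaled to glucose. The documents do not support this. They show no priming error, 3.5 hours of equilibration precede dosing, and the 240–300 min window falls 3.5 + 4 = 7.5 to 3.5 + 5 = 8.5 hours after the prime. The other is that precision is demonstrably being lost. That needs a value of r, and the documents give none.

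**Conclusion.** The point holds as a modest improvement in precision and in protection against imbalance. The planned ANOVA is valid. Pre-dose glucose is a likely prognostic factor on the protocol's own reasoning plus one inferred step, and leaving it out probably costs something.

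Under the stated assumptions, adjustment takes 80% power to about 83–93% for r = 0.3–0.6 with a common slope, but leaves it at about 80–83% if exenatide abolishes the slope. Near r = 0 it costs about one power point. The downside is therefore small and the possible gain useful, the more so because the plan documents no power reserve.

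The word chance presumes random allocation, which the text does not describe. If allocation were not random, imbalance could be systematic, and adjusting for one covariate would not fully cure it.

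**What to change.** Add a sentence to the Data Analysis Plan in Item 6. It should pre-specify the primary dapagliflozin versus dapagliflozin/exenatide comparison as an ANCOVA of EGP change on mean plasma glucose from the −60 to 0 min samples, fitted on those two arms. Pre-dose EGP would enter alongside it if that is also to be adjusted for. If all arms are analysed in one model, let the glucose slope differ by dapagliflozin use, because the proposed mechanism operates only where glucosuria is induced.

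The sentence should be fixed before results are seen, since a covariate chosen afterwards carries little weight. No procedure or sample changes. The cost is one degree of freedom for the two-arm model with glucose alone, and one more if the slope is allowed to differ in an all-arm model.
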